Unfortunately, all those candidate predictors are found on a group comparison level only, and in few studies with small and heterogeneous groups of patients. Therefore, they are not yet applicable on an individual level for treatment choice. Single predictors have not shown a large explaining variance, in depressed or anxiety patients, while combining clinical with MRI data increased explained variance significantly (Serra-Blasco et al., 2016; Månsson et al., 2015; Ball et al., 2014; Doehrmann et al., 2013), using machine-learning models. Machine learning prediction models have also been made for pediatric obsessive-compulsive disorder (Lenhard et al., 2017) and in depressed patients that received electroconvulsive therapy (Redlich and al., 2016). We will explore if candidate predictors of PTSD treatment outcome can be used in a machine-learning model to predict treatment outcome on an individual basis.

[figure not shown]

Figure 1. Brain networks as candidate predictors for treatment outcome in PTSD and PD

Hypotheses B: We hypothesize that non-response to PTSD-treatment and to integrated PTSD-PD treatment, can be individually predicted by a machine-learning model with:

B1. Psychological factors: Cognitive factors (educational level/IQ, working memory, emotion regulation), Affective factors (hyper-arousal: anger, sleep; hyper-arousal: dissociation), and Relational factors (therapeutic alliance, attachment, social support).

B2. Neurobiological factors: Neural factors (volumes ACC and hippocampus, activity and connectivity of salience and negative affect network and ventral and cognitive control network)), and Hormonal/ epigenetic factors (5-HTTLPR, BDNF, cortisol/FKBP5methylation, oxytocin/OXTR).

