4.4 Sample size calculation

A power calculation was made based on Twisk (2007). We assume that PTSD treatment (EMDR or ImRs) have a small effect size (< 0.5) in the complex patient group with PTSD and comorbid

CPD/BPD, while the integrated treatment will show double effect sizes (1.0) (Harned et al., 2014). With a minimal clinical relevant difference of a 0.5SD on the CAPS-5, and the assumptions of a SD of 20.0, an intra-person correlation coefficient of 0.7, 5 follow-up measurements, the needed number to include is 50 persons per condition to reach for 80% power. Expecting a drop-out rate of 25%, we will include 63 persons per arm, or for 4 arms in total 252 persons.

In 2016, approximately 950 new patients were referred to the SC (Amstelveen). From these patients, ca. 450 had PTSD. From these PTSD patients, 168 had a comorbid PD and 188 more were not assessed for personality traits (“Uitgestelde diagnose”). We expect that introducing the assessment of axis II assessments with this study will result in an estimated 300 patients with PTSD and PD per year, and after 33% refusals or exclusions, in an estimated 200 patients possible to include per year. To be sure to include enough patients, we will need to include more patients from another site of the

Sinai Center, i.e. Amersfoort (400 patients, from which 216 PTSD patients, from which an estimated 100 PTSD + PD patients), and extend the inclusion period.

From these 252 patients, 80 will be asked for additional MRI, next to 40 healthy controls (Total sample size = 292). An estimated 40 patients will be available for a second MRI after 6 months (total of 160 scan sessions).

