5. METHODS

5.1 Study parameters/endpoints

5.1.1 Primary outcome parameters

○ Severity of PTSD (DSM-5) as measured with:

- CAPS-5 (Clinician Administered PTSD Scale, Weathers et al., 2014, Boeschoten et al., 2014). The first psychometric evaluation of the CAPS-5 showed good reliability, convergent and divergent validity (Weathers et al., 2017). Severity of PTSD is measured on a continuous scale on the CAPS-5. All 20 symptoms of PTSD from the DSM-5 are assigned a severity score of 0-4. These 20 scores are then summed to calculate total PTSD symptom severity.

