7.1 Primary study parameters

For population description, the CAPS-5, M.I.N.I.-plus, SCID-5-PD, will be used in addition to the CTQ, LEC-5, DERS, ITQ, PAI-BOR, STAS, PSQI, DES-II, WAV, RSQ, CPI, BDI, AUDIT, WHODAS, EQ5D-5L, and Tic-P will be used (see Table 1). The subgroup of patients that underwent MRI will be compared to the rest of the group to test for pretreatment differences in PTSD severity and type/severity of PD.

The primary analysis in the RCTs will be improvement of PTSD symptoms at 3 time points. This primary analysis will include trauma symptom scores at T₀, T₂ and T₄ (CAPS-5, severity score) in a repeated measurements model, a linear mixed model for repeated measurements including at least time points, treatment group, the interaction between time point and treatment, sex, age and severity as fixed factors, baseline score as covariate and subject as random intercept factor. An cAR(1) structure will be used to model the residual covariance matrix. Responders will be defined as participants with a posttest score at least 1 SD below the pretest score (based on Jacobsen and Truax, 1991).

Secondary analyses will examine whether hormonal and epigenetic factors (5-HTTLPR, BDNF, cortisol/FKBP5-methylation, oxytocin/OXTR) mediate the treatment effects. Mediation analyses will include levels of the aforementioned variables on T₀ and T₂ to estimate the direct and indirect paths of casual treatment on the primary and secondary study parameters, through the proposed mediators.

For individual prediction analyses, machine learning techniques (in R: supervised and unsupervised techniques, e.g. the random forest model method) will be applied to separate treatment responders from non-responders based on clinical and neurobiological candidate predictors and in order to define the predictors

contributing most to classification accuracy, calculating sensitivity, specificity, and positive and negative likelihood ratios from the prediction model (Ball et al., 2014).

Candidate predictors that will be used are:

- Psychological factors: Cognitive factors (educational level/IQ, working memory, emotion regulation), Affective factors (hyperarousal: anger, sleep; hyperarousal: dissociation), and Relational factors (therapeutic alliance, attachment, social support);

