- Neurobiological factors: Neural factors (smaller ACC and hippocampus volume, increased right amygdala and ventral ACC activity and de/increased dorsal ACC activity), and Hormonal/ epigenetic factors (5-HTTLPR, BDNF, cortisol/FKBP5-methylation, oxytocin/OXTR).

Questions that will be answered with machine learning in this study are:

1. Does brain activity predict treatment outcome for PTSD and PD (all treatment conditions together; N = 80)
2. Does brain activity predict treatment outcome for PTSD (EMDR and ImRs; N = 40)
3. Does brain activity predict treatment outcome for integrated PD/PTSD treatment (EMDR + DBT and ImRs + SFT, N = 40)
4. Data from the MRI at T2 can be used to predict relapse after treatment for all treatments together (N = 80 if all patients return for a second MRI) or for trauma treatment and integrated treatment separately (N = 40 for both).

fMRI data will be analysed with Statistical Parametric Mapping (SPM) software or FMRIB Software Library (FSL) to map connectivity in the brain. Standard group comparisons will be used to analyse structural and task-related (face recognition) fMRI. First, ANOVA analyses will be performed with patients vs. controls for baseline comparison. Second, full factorial analyses will be conducted in patients-only, with time (baseline vs. end of treatment) and condition (type of treatment) as factors to analyse the effect of treatment on (task-related) brain structure, connectivity and activity. Independent component analysis (ICA; FSL MELODIC) and dual regression analyses will be used to study changes in functional connectivity of brain networks (with a focus on the salience

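### Section 7.1 trains the individual prediction models only on a responder label cut from the continuous CAPS-5, which costs information in the small MRI questions; train on the score and derive the responder call from it

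*Combined protocol and SAP*

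**What the plan says.** Objective B (section 2) is individual prediction of treatment outcome. Section 1 words the hypothesis as "We hypothesize that non-response to PTSD-treatment and to integrated PTSD-PD treatment, can be individually predicted by a machine-learning model with" psychological and neurobiological factors.

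Section 7.1 says machine-learning techniques, with the random forest as the example, "will be applied to separate treatment responders from non-responders based on clinical and neurobiological candidate predictors". The label is given a little earlier: "Responders will be defined as participants with a posttest score at least 1 SD below the pretest score". Performance is to be reported by "calculating sensitivity, specificity, and positive and negative likelihood ratios from the prediction model". Section 5.1.1 describes the underlying outcome differently: "Severity of PTSD is measured on a continuous scale on the CAPS-5". The mixed model for the two RCTs, also in 7.1, uses it in that form.

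The MRI questions in 7.1 carry their own sample sizes. Question 1 is "Does brain activity predict treatment outcome for PTSD and PD (all treatment conditions together; N = 80", question 2 is "Does brain activity predict treatment outcome for PTSD (EMDR and ImRs; N = 40", and question 3 repeats this for integrated treatment, also with 40 patients. Question 4 concerns relapse. Section 4.4 sets the whole trial at "for 4 arms in total 252 persons"; no separate number is given for the psychological or hormonal and epigenetic predictors.

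Four things are not stated: which SD defines response, which visit is the posttest, why the model must be trained on the label, and any test, significance level, effect size or power for the prediction analyses. That the label is cut from the CAPS-5, and that it is the outcome in questions 1 to 3, are fair inferences from the surrounding text and not explicit statements.

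**The concern.** Cutting the score before training removes information that the model could learn from. With a 20-point cut, a patient who improves by 19 points is treated like one who worsens, and a 21-point drop counts the same as a 40-point drop. The reliable-change reference cited for the label explains where the threshold lies. It does not explain why the model should see nothing but the threshold.

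The loss matters most where patients are few, and the MRI questions have 80 or 40. A real predictor is then more easily missed, and the resulting instrument ranks patients somewhat less well. The intended clinical output does not require this, because a model trained on the score can still produce a responder call.

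**Working it through.** **Inputs.** Section 4.4: SD 20, within-person correlation 0.7, 5 follow-up measurements, difference 0.5 SD = 10 points, effects of 0.5 (the plan says below 0.5) and 1.0. Section 7.1: N = 80 and 40, cut of 1 SD. Section 1: at least 30-44% of PTSD patients do not respond sufficiently or drop out. Assumed here: two-sided 5%; the effects read as mean drops of 10 and 20 points; the 0.7 applied between pretest and posttest; predictor-outcome correlations r of 0.2 to 0.5.

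**Step 1: the plan's only power figure.** n per condition = 2(z₀.₉₇₅ + z₀.₈₀)² SD² [1 + (T − 1)ρ] / (T δ²) = 2 × 7.85 × 400 × (1 + 4 × 0.7) / (5 × 100) = 47.7, so 48, against the plan's 50. The inputs are therefore usable. This figure concerns the RCT comparison; there is no counterpart for prediction.

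**Step 2: responder shares.** SD of change = 20 × √(2 × (1 − 0.7)) = 15.5.
- PTSD treatment alone: 1 − Φ((20 − 10)/15.5) = 0.26, or about 10 of 40.
- Integrated treatment: 1 − Φ(0) = 0.50, or 20 of 40.
- Pooled: (0.26 + 0.50)/2 = 0.38.
- From the background text: 56-70% responders.

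If 1 SD meant the SD of change, 15.5 points, the shares would be 1 − Φ((15.5 − 10)/15.5) = 0.36 and Φ((20 − 15.5)/15.5) = 0.61. All of these lie within 26-70%.

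**Step 3: information kept.** For a cut leaving share p as responders, the asymptotic relative efficiency is φ(z_p)² / [p(1 − p)]. This gives 0.55 at 26%, 0.62 at 38%, 0.64 at 50%, 0.63 at 56% and 0.58 at 70%.

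**Step 4: single-predictor power.** Simulated test of one normal predictor against the full score and against the label, 10,000 runs per cell; entries are score vs label (loss in points).

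| Setting | r = 0.2 | r = 0.3 | r = 0.4 | r = 0.5 |
|---|---|---|---|---|
| N = 80, 38% respond | 42.8 vs 28.7 (14.1) | 78.2 vs 56.6 (21.6) | 96.0 vs 82.3 (13.7) | 99.8 vs 96.4 (3.4) |
| N = 40, 26% respond | 23.2 vs 14.9 (8.4) | 46.6 vs 27.0 (19.6) | 74.9 vs 47.6 (27.2) | 92.3 vs 67.3 (25.0) |
| N = 40, 50% respond | 23.0 vs 16.6 (6.4) | 47.7 vs 32.6 (15.1) | 74.2 vs 53.3 (20.9) | 92.3 vs 76.0 (16.3) |

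The smallest loss, 2.8 points, is at N = 80, r = 0.5 and 50% responders. Repeat runs move entries by up to about a point, which puts the top at 28.

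**Step 5: predicting the same responder status.** Random forests were trained on the label or on the score (10 predictors, assumed R² = 0.30) and scored on the same label in 2,000 new patients. AUC was 0.63 vs 0.65 at N = 40 and 0.65-0.66 vs 0.68 at N = 80. Accuracy was 0.5 to 1.6 points higher with the score. Logistic against linear models differed by 0.02-0.03 in AUC. Other assumed R² values (0.20 and 0.35) took the gain to at most 0.04.

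**The case against.** **The binary target is deliberate.** Hypothesis B names non-response, and a classifier trained on the hypothesised outcome is a legitimate choice. The simulations also assume linear, normal effects, which favour the score. This stands as a reason to keep the classifier as a sensitivity analysis. It does not explain why the score should be left unused in training.

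**Simply applying the 1-SD cut to predicted scores does harm.** Predictions shrink toward the mean. In the PTSD-only setting, with R² = 0.20 and the true model known, predicted drops have SD 15.5 × √0.20 = 6.9. Only 1 − Φ(10/6.9) = 7.5% of patients would be called responders, against a true 26%, and sensitivity would be 17%. In simulated forests at N = 40, sensitivity was 2-8% with the raw cut against 14-17% with the planned classifier; specificity was 97-99% against 92-93%. This stands and shapes the fix. With the threshold matched to the observed response rate, the score-trained model did better on both measures in all six settings run, by about 1 to 2 points each.

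**A reader might infer a power loss of up to about 35 points.** Simulated power to beat chance with a random forest can suggest this, but it compares out-of-bag AUC for a label with out-of-bag rank correlation for a score. Those are different statistics on different targets. The label's power at N = 80 and R² = 0.20 came out at 23% in one simulation and 42% in another. For a single predictor, 35 points needs a split near 85/15, outside the 26-70% that the documents support.

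**A reader might also apply N = 80 or 40 to all prediction analyses.** Section 7.1 gives those numbers only for the MRI questions.

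**Conclusion.** The point holds for MRI questions 1 to 3. The plan trains on a dichotomised score, plans no continuous prediction model and gives no reason. The information kept, 55-64%, depends on the responder share and on approximate normality. The power loss of about 3 to 28 points is conditional on the assumed correlations and the assumed test. It is smallest for strong predictors at N = 80 and largest at N = 40 with 26% responders. The loss in AUC, about 0.02-0.04, is real but modest.

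The documents do not support saying that the plan loses a fixed amount of power, since it specifies no test for prediction. Nor do they support carrying these figures to question 4, which concerns relapse and not this cut, or to predictors measured in the wider sample of 252. The present plan is usable; the change is a worthwhile, inexpensive gain for a primary objective.

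**What to change.** In section 7.1:

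1. Train the prediction models on the continuous T4 CAPS-5 score, with the T0 CAPS-5 score among the predictors.
2. Base the above-chance test on predicted against observed score, by cross-validation or out-of-bag, and state its significance level.
3. Derive the responder call from that model at a threshold set inside the cross-validation, for example matched to the training response rate, or using a predicted probability of a 1-SD drop. Do not apply the raw 1-SD cut to the predicted scores.
4. Report sensitivity, specificity and likelihood ratios at that threshold, as already planned.
5. Keep the direct responder classifier as a sensitivity analysis.
6. State which SD and which visit define response.

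This takes a few lines of text, one more model run and a threshold step to explain. It needs no new patients, visits or measurements, and leaves hypothesis B unchanged.

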4. STUDY POPULATION

4.1 Population

The study population consists of all patients between 18-65 years old, referred to the SC with comorbid PTSD and PD, who are willing to participate in the study (informed consent); N = 252 patients (see 4.4), of which sub-group of 80 patients (N = 40 Condition 1 + 40 Condition 2) will participate in the MRI study (before and after treatment). For baseline MRI comparison, extra 40 healthy controls, matched on age, gender and educational level, will be recruited also for the MRI study via advertisements in local newspapers and through hersenonderzoek.nl. In total, 292 persons will be included in this study.

A pilot episode will be introduced (September – December 2017) to test the feasibility of the study and inclusion rate. Feasibility is enhanced by the opportunity to build on the established expertise of the academic research group in Arkin – Research and VUmc in conducting effect studies, longitudinal and neurobiological studies.

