5.2 Randomisation, blinding and treatment allocation

5.2.1 Randomization

An independent central research assistant will randomize participants to condition after checking all in- and exclusion criteria. Randomization will be based on block randomization (n=4 per block) per site, to guarantee a balance between conditions per site and over time. For both RCTs there will be a separate randomization procedure depending on comorbid PD diagnosis:

- A1. If PTSD + BPD: EMDR vs. integrated DBT-EMDR
- A2. If PTSD + CPD: ImRs vs. integrated SFT-ImRs.

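### The brain-prediction questions pool the two RCTs with no term, stratum or benchmark for RCT, so a classifier that only recognises PD type can look predictive if response rates differ between the RCTs

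*Combined protocol and SAP*

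**What the plan says.** Section 5.2.1 sets the route into each trial: "For both RCTs there will be a separate randomization procedure depending on comorbid PD diagnosis". For A1 the rule is "If PTSD + BPD: EMDR vs. integrated DBT-EMDR"; for A2, cluster C patients are randomised between ImRs and integrated SFT-ImRs. Randomisation therefore acts only within a PD group.

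Section 7.1 then poses the brain questions across both groups. Question 1: "Does brain activity predict treatment outcome for PTSD and PD (all treatment conditions together; N = 80". Question 2: "Does brain activity predict treatment outcome for PTSD (EMDR and ImRs; N = 40". Question 3: "Does brain activity predict treatment outcome for integrated PD/PTSD treatment (EMDR + DBT and ImRs + SFT, N = 40".

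The candidate predictors listed in 7.1 include neither RCT nor PD type. The outputs are sensitivity, specificity and likelihood ratios, with no pass threshold, no stratified validation and no benchmark model. On the imaging sample, section 4.1 says: "of which sub-group of 80 patients (N = 40 Condition 1 + 40 Condition 2) will participate in the MRI study". I read the two conditions as trauma-only and integrated treatment, as in questions 2 and 3. No borderline/cluster C split is given.

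PD type appears elsewhere in section 7, in the descriptive tables and in the comparison of MRI patients with the rest of the sample. Neither is part of the classifier.

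**The concern.** Within each pooled set, the diagnosis that determined the RCT and the trauma-therapy modality are completely tied, and not by randomisation. If one RCT has a higher response rate, any brain feature that distinguishes its patients from those of the other RCT will be associated with response in the pooled data, even if it carries no information among patients of the same RCT.

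Section 2 lists individual prediction among the primary objectives, with the aim of improving treatment indication. PD diagnosis is already known when a patient is allocated to an RCT. A pooled result therefore could not show whether a scan adds to that diagnosis, or whether it has picked up PD type or the EMDR/ImRs difference. Section 5.3 poses the psychological prediction questions separately for A1 and A2; the brain questions are not posed that way, and no reason is given.

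**Working it through.** **The plan's own figures.** The one computed sample size is 50 per condition (section 4.4). With difference 0.5 × 20 = 10, SD 20, correlation 0.7, five measurements, 80% power and two-sided alpha 5% (alpha is assumed; the plan gives none), n = 2(1.96 + 0.84)² × 20² × (1 + 4 × 0.7) / (5 × 10²) = 47.7, so 48. That agrees closely with 50. It concerns the RCT comparison only. The MRI figures (40 + 40 = 80) have no calculation behind them, and no target accuracy is stated.

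**Inputs for the check.** The documents give no response rates by PD type, so all rates below are scenarios. The pair 56% and 70% comes from the 30–44% non-response quoted in section 1. The pair 40% and 80% is an outer bound: it is a remission contrast from section 1 between integrated DBT-PTSD treatment and DBT alone, not between PD types. An equal borderline/cluster C split is assumed.

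**A rule that knows only PD type.** Let p1 ≤ p2 be the response rates in the two RCTs, and let the rule call everyone in the higher-rate RCT a responder.

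- Sensitivity = p2 / (p1 + p2)
- Specificity = (1 − p1) / (2 − p1 − p2)
- AUC = (sensitivity + specificity) / 2
- Accuracy = 0.5 p2 + 0.5 (1 − p1)

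At 56/70%: sensitivity 0.70/1.26 = 0.556, specificity 0.44/0.74 = 0.595, AUC 0.575. At 40/80%: 0.80/1.20 = 0.667, 0.60/0.80 = 0.750, AUC 0.71, and positive likelihood ratio 0.667/0.250 = 2.67.

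The last two columns give the chance that PD type and response are associated at two-sided 5% (chi-square).

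| Response rates | AUC | Accuracy | Majority-class rate | N = 40 | N = 80 |
|---|---|---|---|---|---|
| 60/60% | 0.50 | 50% | 60% | 5% | 5% |
| 56/70% | 0.575 | 57% | 63% | 15% | 25% |
| 50/70% | 0.60 | 60% | 60% | 25% | 46% |
| 40/60% | 0.60 | 60% | 50% | not run | not run |
| 30/70% | 0.70 | 70% | 50% | not run | not run |
| 40/80% | 0.71 | 70% | 60% | 75% | 97% |

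Fisher's test gives lower figures, for example 65% and 95% in the last row. With a 25/75 split instead of an equal one, AUC is about 0.55 to 0.68 over the range from 56/70% to 40/80%. Within either RCT the rule gives every patient the same prediction, so its AUC there is 0.50 by construction.

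**A noisier brain score.** In simulation (1,500 runs, one-sided 5% permutation test), a score on which the PD types differ by 1 SD, with no other information, was declared predictive in 5% (N = 40) and 5% (N = 80) of runs at 60/60%. At 40/80% the figures were 32% and 51%, with AUC 0.61.

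**After the repair.** Permuting within RCT brought these rates to about 4–6% in every scenario simulated (60/60%, 56/70%, 50/70%, 40/80%), with mean within-RCT AUC 0.50.

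**Patients with an outcome label.** Response needs a posttest score, in context the CAPS-5. Section 4.4 plans: "Expecting a drop-out rate of 25%, we will include 63 persons per arm". If that 25% held in the MRI subgroup and dropouts had no posttest CAPS-5, questions 1 to 3 would have 80 × 0.75 = 60, 40 × 0.75 = 30 and 30 labelled patients.

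**The case against.** The strongest reply is that nothing in the documents says the two conditions hold. No response rates by PD type are given, and no claim is made that brain features separate borderline from cluster C patients. Section 4.2 admits patients one symptom short of a diagnosis, and mixed presentations are eligible, which makes PD type harder to recognise from a scan. At 56/70% even a perfect PD-type rule is less accurate than calling everyone a responder. This stands. A reader might infer that a PD-type classifier will pass as a predictor; the documents do not support that, and they set no pass criterion.

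It can also be said that PD information is not wholly absent, since section 5.1.4 lists the PAI-BOR among the psychological predictors. But the list in 7.1 does not name it, it measures borderline severity and not RCT, and it supplies no benchmark for the brain questions.

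Objective B addresses a pooled PTSD-with-PD population, and section 1 describes the machine learning as exploratory. Pooling is therefore legitimate in itself, and PD type may be a real predictor of outcome. What remains is that a pooled figure alone cannot show what the scan adds.

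Finally, the 25% dropout is the assumption for the RCTs, not for the MRI subgroup. Section 5.6 keeps treatment dropouts in follow-up, although it gives priority to the PCL-5 and OQ-45. The CAPS-5 is also taken at T2, and posttest is not tied to T4. So 60, 30 and 30 is an illustration, not a corrected N.

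**Conclusion.** The point holds as a conditional weakness. Questions 1 to 3 pool the RCTs, diagnosis fixes the RCT and the trauma-therapy modality, and nothing in the classifier separates prediction of response from recognition of PD type. The size runs from nothing (AUC 0.50 at equal response rates) to about 0.70 at 30/70% or 40/80%, under assumed rates and an equal split.

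Two further inferences should be avoided. The randomised contrast, trauma-only versus integrated, lies within each RCT and is not tied to PD type; the gap concerns PD type and EMDR versus ImRs. And the documents give no basis for an MRI target per RCT; they simply do not state the split. Because the objective is listed as primary and the repair protects whatever the true rates are, the change should be made.

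**What to change.** In section 7.1:

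- Fit a reference model with RCT, plus arm in question 1.
- Stratify all resampling and permutation by RCT.
- Report performance within A1 and within A2, beside the majority-class rate.
- Claim brain-based prediction only for the gain over the reference model.
- Report the borderline/cluster C split of the MRI subgroup.
- State N for questions 1 to 3 as the number of scanned patients who have a posttest CAPS-5.

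RCT is already coded in every subject number (section 9.1: 45 for borderline, 46 for cluster C), so no new data are needed. The cost is some analysis work, a few extra tables and possibly a lower pooled accuracy. Within-RCT estimates will be imprecise: with an equal split, the stated N gives about 40 patients per RCT in question 1 and about 20 in questions 2 and 3, before any loss of outcome data.
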